## ***Statistical analysis plan***

Sample size determination. Sample size is based on statistical power analyses for the primary hypothesis based on single primary outcome (opioid abstinence without MOUD). A conservative approach was used to preserve power with a smaller effect size than observed from prior uncontrolled, non-blinded intervention studies with the NET Device. Power analyses examined sample sizes required to detect clinically meaningful group differences between sham and active groups. This represents standardized difference between the two groups after adjusting for the effect of the covariate “duration of inpatient residence” (which is capped at 28 days). Sample size determination was carried out *via* simulation in R-software; 5000 iterations were run in which group means were generated using a mixed-effect additive model. Sample size is a function of hypothesized effect size (standardized group difference) and the sign and magnitude of the regression coefficient (duration of inpatient residence). With projected N=100 (enrolled) there will be sufficient power to detect a standardized effect size of 0.45 or higher.

Missing data. In this ITT design, a participant is “included” (becomes part of the evaluable ITT data set) when he/she completes 1-hr of device use. We expect only 5% attrition, i.e. for 100 participants who complete 1-hr of device use, we expect to consent 105 individuals. A comparable trial of a

percutaneous electrical stimulation device for treating opioid withdrawal symptoms found that 71 of 73 enrolled participants completed 1-hr of device use, only 2.8% attrition [18]. **Table 1** explains how missing data are handled, i.e. for the primary efficacy endpoint, missing data are imputed as “not opioid abstinent without MOUD”. The definition of the primary endpoint (“opioid abstinence without MOUD”) and secondary endpoint (“non-opioid abstinence”) thus covers any intermittent missing values and loss to follow-up, and is not expected to impact power of the primary analysis. Premature study termination (e.g., death, relocation, or adverse events) may result in missing data, although this attrition is expected to be low. The projected sample size (N=125) was increased to cover unforeseen events.

Participant withdrawal. Participants can withdraw from the study at any time on request. Discontinuation of device use prior to completing the minimum 1-hr treatment period constitutes withdrawal from the study. The investigator may discontinue or withdraw a participant from the study for the following reasons: (1) significant study intervention non-compliance; (2) if any clinical adverse event (AE), laboratory abnormality, or other medical condition or situation occurs such that continued participation in the study is not in the best interest of the participant; (3) disease progression which requires discontinuation of the study intervention; (4) if the participant meets an exclusion criterion (either newly developed or not previously recognized) that precludes further study participation; or (5) participant is unable to receive treatment following enrollment.

Participants who sign the informed consent form and are randomized but do not receive the study intervention will be replaced. Participants who sign the informed consent form, are randomized, receive the study intervention, and subsequently withdraw or are withdrawn, will be replaced.

Participants who withdraw from the study will receive TAU as defined by treatment staff (who are independent of the research staff), where such care may include MOUD.

Lost to follow-up. A participant is considered lost to follow-up if s/he becomes unavailable for all video assessments following discharge from the inpatient environment.

Populations for analysis. The ITT analysis dataset and the safety analysis dataset will contain all randomized participants. The per-protocol analysis dataset will contain the subset of the ITT dataset who: (1) present with a COWS score of moderate or above; (2) receive at least 1 hr treatment from the device; and (3) complete at least one post-discharge video interview.

Efficacy endpoints. The primary analysis will assume that data came from a mixed-effect linear model. Each model will include a random intercept, fixed effect for treatment, participant-specific random effect and covariate corresponding to duration of inpatient residence. The primary hypothesis involves testing the main effect for treatment difference between the groups (sham vs. active). A likelihood ratio test will examine the group effect focusing on the primary hypothesis.

Secondary endpoint analyses are not powered, but may be used to demonstrate additional benefits of the treatment, provided it has been demonstrated that the primary endpoint shows clear statistical significance, as well as clinical meaningful benefits of the treatment [19]. Analysis of the secondary endpoint resembles primary endpoint analysis, using mixed-effect model testing for the between-group main effect.

Given that participants can control the level of device stimulation, exploratory regression analyses will seek to identify potential relationships between device utilization (e.g. number of minutes device ‘on’ [non-zero intensity], average intensity while device ‘on’) and efficacy endpoints.

Expected outcomes. We selected a single primary outcome (abstinence without MOUD). From our past experience at this same treatment facility, the expected group means for sham and NET arms are 0.48 and 3.97 weeks of average opioid abstinence with standard deviations 1.19 and 3.46, respectively. This results in effect size of 1.12. This effect size based on pilot data is rather large,

which is often the case due to limited scope of the pilot study. Thus, we took a conservative approach as suggested by Kraemer et al. [20] with moderate effect size of 0.45.

Safety endpoints. Secondary safety endpoints (AEs, SAEs, ADEs, SADEs, UADEs and device deficiencies) will be summarized using descriptive statistics.

Subgroup analysis. The analysis will stratify by sex (male/female) and non-opioid SUD (presence/absence). The expected outcome is that allocation on those variables will be balanced between the two groups. It is not anticipated that the primary outcome (opioid abstinence without MOUD) will differ across these subgroups. If significant baseline group imbalance is detected on any variable and its correlation with outcome ( $\geq 0.30$ ), that variable will be included as a covariate in the inferential analyses. If systematic variation is noted by any subgroups for primary or secondary outcomes, further exploration will be conducted via cluster analysis.

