### ***Study design***

This ITT, randomized, single-site trial uses a superiority design that compares active treatment to sham control. This trial will evaluate efficacy and safety endpoints during opioid discontinuation within an inpatient setting, and subsequent outpatient assessment of opioid and non-opioid substance use following discharge (primary and secondary endpoints, respectively). Fifty participants will be randomized to each of the two treatment arms (active and sham) and prospectively followed. **Figure 2** illustrates the study schema. **Figure 3** illustrates the schedule of activities.

As the platform for this trial, all participants receive treatment as usual (TAU), except MOUD, which they choose (as part of informed consent) not to receive as a condition of inclusion in this study. Participants could experience clinical deterioration during inpatient discontinuation of illicit opioids, prescribed opioid agonist medications (buprenorphine, methadone), and other illicit substances. Participants are instructed that device use (active or sham treatment) is self-administered, they may discontinue device use at any time and for any reason and can receive TAU for their clinical condition including MOUD and comfort medications.

The rationale for the minimum 1-hour device treatment period is to ensure a controlled degree of exposure to the device (active or sham) for all participants; based on prior open-label studies, the active device produces benefits in about 15-20 min. Completing this 1-hr period triggers study follow-up assessments. The rationale for the 7-day maximum device treatment period is to limit variability in the duration of exposure (to be treated as a covariate in analyses); as **Figure 1** indicates, the majority of participants stop active device use after about 7 days.

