During a given week, oral fluid samples and self/pharmacy reports that both indicate no illicit opioid, methadone, buprenorphine, or naltrexone use will be considered "opioid-abstinence without MOUD". Cumulative distribution function, time (days) to first use of illicit opioids, time (days) to first use of MOUD, and duration (weeks) of continuous abstinence without MOUD will be evaluated as supportive outcomes. Response profiles for each treatment arm are based on each participant's individual rates of weekly illicit opioid or MOUD use, including negative oral fluid results and daily

self (TLFB) of illicit opioid or MOUD use/non-use. **Table 1** presents explanatory cases of the primary efficacy endpoint measurement. The null hypothesis is that “opioid abstinence without MOUD” will not significantly differ between active and sham groups, whereas the alternative hypothesis is that “opioid abstinence without MOUD” will be superior in the active (relative to sham) treatment arm.

The secondary efficacy endpoint is each participant’s percentage of non-opioid drug-free weeks during the 12-week outpatient period. Non-opioids assessed include cocaine, sedatives, and stimulants. Use of alcohol and cannabis will be measured, but are not included in the secondary efficacy analysis, due to their legal status. Response profiles for each arm are based on each participant’s individual rates of weekly abstinence data, including negative oral fluid results and daily self-reports of non-opioid drug use/non-use (TLFB).

The secondary safety endpoint is the prevalence of all adverse events (AEs), serious adverse events (SAEs), adverse device effects (ADEs), serious adverse device effects (SADEs), unanticipated adverse device effects (UADEs), and device deficiencies.

Supportive and exploratory measures. Treatment retention will be measured throughout the inpatient and outpatient phases. Self-stimulation intensity (in 5-min bins), duration, and device on/off data from each NET Device are automatically transmitted to a computer server and processed offline. Opioid withdrawal symptoms, craving severity, and positive/negative affect are measured daily during the first inpatient week. Measures of depression, anxiety and stress, sleepiness, and health-related quality of life are obtained at the conclusion of inpatient and outpatient phases.

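### Stopping the device within the first hour counts as leaving the study, so planned safety follow-up ends for an exposed participant who remains in the safety set

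*Combined protocol and SAP*

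**What the plan says.** Four parts of the combined protocol and SAP bear on this.

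- **Withdrawal.** Statistical analysis plan, Participant withdrawal: "Discontinuation of device use prior to completing the minimum 1-hr treatment period constitutes withdrawal from the study". The same part says that withdrawn participants pass to usual care under staff outside the research team and are replaced, including those who had already received the intervention.
- **Follow-up trigger.** Study design: "Completing this 1-hr period triggers study follow-up assessments". The same section tells participants that "they may discontinue device use at any time and for any reason".
- **Analysis set.** Populations for analysis: "The ITT analysis dataset and the safety analysis dataset will contain all randomized participants". The Missing data paragraph is narrower: a participant "becomes part of the evaluable ITT data set) when he/she completes 1-hr of device use".
- **Safety endpoint and analysis.** Outcome measures makes the prevalence of adverse events, device effects and device deficiencies the secondary safety endpoint. The Safety endpoints paragraph says only that these "will be summarized using descriptive statistics". The missing-data rule that is given concerns the abstinence endpoints.

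In Figure 3, as extracted, adverse events are marked from Day 1 Baseline, the column in which treatment is first administered. Device tolerability and device deficiencies are first marked at Day 1, One Hour Elapsed.

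**The concern.** Early stopping is one of the ways in which poor tolerability of a self-administered device would show itself. Under the stated rule, someone who is switched on and takes the device off within the hour ceases to be a study participant and never reaches the point at which follow-up begins. The planned record of what happened to that person then stops, although the person still counts in the safety denominator.

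At stake is the completeness of a named endpoint, and with it the planned follow-up of any effect that led to the stop. Only the active arm receives current, so early stops caused by current can arise only there. The trial has no data safety monitoring board that might otherwise notice a pattern of early stops.

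The text also conflicts with itself on what stopping means. Study design treats stopping as a free choice within the trial, and Participant selection criteria separates ending stimulation from dropping out. Participant withdrawal merges the two for the first hour.

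**Working it through.** **1. Trace one exposed participant who stops at, say, 20 minutes (time chosen for illustration).**

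- Switch-on: Figure 3 marks treatment and adverse events in the Day 1 Baseline column, so an event at this stage can be entered.
- 20 minutes: the participant is withdrawn from the study under the Participant withdrawal rule.
- 60 minutes: the first device-tolerability and device-deficiency assessments fall due and are not reached.
- Afterwards: follow-up is not triggered, and no early-termination safety visit or adverse-event resolution check is described.
- Analysis: the participant is in the safety set, because all randomized participants are.

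**2. Adverse-event contacts lost after baseline.** From Figure 3, taking one contact per day on Days 2–7: 1 (one hour) + 6 (Days 2–7) + 2 (Days 14 and 21) + 1 (Day 28) + 12 (outpatient weeks) = 22.

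**3. Reproduce the plan's own figure.** The Missing data paragraph expects 5% attrition and 105 people consented for 100 who complete the hour. 100 × (1 + 0.05) = 105, as stated. Dividing instead gives 100 / 0.95 = 105.3, rounded up to 106; the difference does not matter here. The comparison study is quoted as 71 of 73 completing, with 2.8% attrition. 2/71 = 2.8%; with all 73 enrolled as the denominator, 2/73 = 2.7%.

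**4. How many people.** 105 − 100 = 5, and 5/105 = 4.8%. At the comparison study's rate, 105 × 2/73 = 2.9, or about 3.

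**5. Bound on the overall event rate.** Let p be the event rate in the 100 completers; the documents give no value, so p is an assumption.

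- No event captured in the 5: 100p / 105.
- All 5 have an event and it is captured: (100p + 5) / 105.
- Difference: 5/105 = 4.8 points, whatever p is.

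| Assumed p | None captured | All captured |
|---|---|---|
| 0% | 0.0% | 4.8% |
| 5% | 4.8% | 9.5% |
| 10% | 9.5% | 14.3% |
| 20% | 19.0% | 23.8% |

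At 2/73 the bound is 2.7 points.

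**6. Bound within one arm.** With 50 completers and k early stoppers in that arm, the bound is k / (50 + k): 1/51 = 2.0, 2/52 = 3.8, 3/53 = 5.7 and 5/55 = 9.1 points.

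**The case against.** The strongest reply is that the schedule does capture what matters. Adverse events are marked from Day 1 Baseline, the endpoint covers all adverse events and not only those found at scheduled contacts, and an adverse event is itself a listed ground for withdrawal by the investigator. An event that makes someone remove the device can therefore be written down. This stands, and it rules out the reading that early stoppers are never assessed. It does not reach what happens after the stop, nor the tolerability and device-deficiency items, which have no mark before one hour. The Baseline column also holds pre-treatment measures, so it does not clearly commit the site to recording events after switch-on. All of this rests on column positions in extracted text.

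A reader might also infer that early stoppers are counted as event-free. No passage says so. That would follow only if unobserved events were treated as absent in the all-randomized denominator; the plan is silent.

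Nor do the documents show that any bias must favour the device. Both arms wear the same electrodes, so a skin reaction can occur under sham, and a sham participant in withdrawal may stop for lack of benefit. Users also set their own intensity, so discomfort need not lead to a stop. The asymmetry is confined to stops caused by current.

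Finally, one might extend the point to the investigator's withdrawal grounds, such as "disease progression which requires discontinuation of the study intervention". Those grounds are discretionary and concern clinical management, and nothing there says that event collection ends. They are not part of this point.

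**Conclusion.** The gap is real and narrow. Followed as written, the plan ends scheduled safety collection in exposed people who stop within the hour, keeps them in the safety set, and gives no rule for their incomplete data. Harms that emerge or evolve after an early stop can be under-counted.

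The size cannot be computed, because the documents give neither an adverse-event rate nor the share of early stops due to harm. On the plan's own 5%, about 5 of 105 people at most are affected, which gives the bounds of 4.8 points overall and 9.1 points if all are in one arm. These are extremes: they assume that all five were exposed, that all had an event and that none was captured. The five are consented people who did not complete the hour, so they may include participants dis-enrolled because the withdrawal score was not reached, who never had the device on.

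A reader might take the projected N of 125 to imply up to 25 early stops. The plan says that increase covers unforeseen events in general, so it does not forecast early device stops.

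**What to change.** For safety data, define stopping before one hour as discontinuation of the device and not as the end of data collection. Specifically:

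- start adverse-event and device-deficiency collection at first device-on;
- carry out the One Hour Elapsed adverse-event, tolerability and device-deficiency assessments at the time of any earlier stop;
- continue the scheduled adverse-event contacts unless the participant withdraws consent to follow-up;
- report the number of early stops and their reasons by arm, and state how participants with incomplete safety data are handled.

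Reconcile Study design, Participant selection criteria and Participant withdrawal on device discontinuation versus study withdrawal, leaving the clinical grounds for stopping treatment as they are. The two descriptions of the ITT set, in Missing data and in Populations for analysis, need reconciling at the same time.

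The cost is protocol wording, a change to the case-report-form trigger, and about five more participants, or fewer, followed on visits the trial already runs. The reported event rate may become slightly less favourable.

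### A device stop before 1 hour ends study participation, and the plan's two ITT definitions disagree on whether that randomized participant is analysed

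*Combined protocol and SAP*

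**What the plan says.** All of this is in the combined protocol and SAP.

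- **Automatic rule** (Statistical analysis plan, Participant withdrawal): "Discontinuation of device use prior to completing the minimum 1-hr treatment period constitutes withdrawal from the study".
- **Discretionary rule** (same paragraph): "The investigator may discontinue or withdraw a participant from the study for the following reasons: (1) significant study intervention non-compliance". Reason 3 is "disease progression which requires discontinuation of the study intervention" and reason 5 is "participant is unable to receive treatment following enrollment". Reason 2 separately covers any adverse event, laboratory finding or other situation in which staying in the study is against the participant's interest.
- **Replacement** (same heading): this applies to those who "are randomized but do not receive the study intervention will be replaced" and also to those who "receive the study intervention, and subsequently withdraw or are withdrawn, will be replaced".
- **Start of follow-up** (Study design): completing the first hour is what sets the follow-up assessments in motion.
- **ITT set, first statement** (Missing data): a participant enters the evaluable ITT set on completing 1 hour of device use.
- **ITT set, second statement** (Populations for analysis): "The ITT analysis dataset and the safety analysis dataset will contain all randomized participants". The per-protocol subset then adds its own 1-hour condition, which would be redundant if ITT already required it.
- **Timing** (NET Device description; Outcome measures): the device is used for at most 7 days. The primary endpoint is measured over the 12 outpatient weeks after discharge.

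No section describes outcome or adverse-event collection after a withdrawal.

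**The concern.** The trial asks whether up to a week of stimulation changes abstinence over the following 12 outpatient weeks. Someone who stops after 50 minutes has been randomized and can still be phoned and tested every week, because the outcome needs no device. Ending study participation at that moment discards an observable outcome.

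The analysis sets do not settle what happens next. Under the Missing data text the person never enters ITT, so the comparison is conditioned on an event after randomization. Under Populations for analysis the person stays in, and all 12 weeks are imputed as not abstinent. Two statisticians could follow this plan and analyse different populations.

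Reasons 1, 3 and 5 raise the follow-up question for people past the first hour. Reason 1 concerns the intervention only, and reasons 3 and 5 do so in part. Reason 2 already provides a way out of follow-up when staying in is not in the participant's interest. Reason 1 also turns on the word significant, which is undefined for a device that participants may set and stop as they wish.

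Adverse events are a secondary endpoint, and whether they are still collected from these people is left open.

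**Working it through.** **1. The rules side by side**

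| Randomized participant | Study status | Follow-up | ITT by Missing data | ITT by Populations for analysis |
|---|---|---|---|---|
| Stops at 50 minutes | Withdrawn, replaced | Not triggered | Out | In |
| Stops at 70 minutes by own choice | Not withdrawn | Triggered | In | In |
| Passes 1 hour, then withdrawn under reason 1, 3 or 5 | Withdrawn, replaced | Continuation not described | In | In |

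The two ITT definitions conflict only in the first row. In the third row the issue is imputation in place of observation.

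**2. The plan's attrition figure**

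100 × 1.05 = 105 consented, as the plan states (100/0.95 would give 106). The comparable trial had 71 of 73 reaching 1 hour: 2/71 = 2.8% as printed, 2/73 = 2.7%. The 5% runs from consent to 1 hour, so it can include people dis-enrolled because COWS never reached 13. It is therefore at most an upper bound on early device stopping. No rate is given for reasons 1, 3 and 5; 10% is my assumed high case.

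**3. Effect of scoring affected participants 0/12**

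Inputs from Expected outcomes: sham mean 0.48 weeks, SDs 1.19 and 3.46; design effect size 0.45.

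- Pooled SD = √((1.19² + 3.46²)/2) = 2.587.
- Difference = 0.45 × 2.587 = 1.16 weeks, so the active mean is 0.48 + 1.16 = 1.64.
- With a share w scored 0: mean′ = (1−w)m; variance′ = (1−w)(s² + m²) − mean′²; d′ = difference in mean′ / √(average variance′).
- Example, active arm only, w = 5%: mean′ = 0.95 × 1.644 = 1.562; variance′ = 0.95 × (11.972 + 2.704) − 1.562² = 11.50; d′ = (1.562 − 0.48)/√((11.50 + 1.416)/2) = 1.082/2.541 = 0.426.

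| Affected arm | 2.8% | 5% | 10% |
|---|---|---|---|
| Both equally | 0.442 | 0.436 | 0.422 |
| Active only | 0.436 | 0.426 | 0.401 |
| Sham only | 0.456 | 0.460 | 0.471 |

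This assumes that affected participants would otherwise have averaged like their arm. The plan's 0.45 is defined after covariate adjustment, so the raw SD is also an assumption. With SD 2.165 (assumed covariate R² of 0.3), active only gives 0.435, 0.424, 0.397. With SD 3.116 (the plan's 1.12 = 3.49/SD), it gives 0.438, 0.428, 0.405. The active SD of 3.46 belongs to a pilot mean of 3.97 and is kept here at a mean of 1.64; this was not varied.

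**4. What following them would change**

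Suppose the affected people are in the active arm and would have done like sham (mean 0.48, SD 1.19).

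| Handling | 2.8% | 5% | 10% |
|---|---|---|---|
| Followed and analysed | 0.442 | 0.435 | 0.420 |
| Kept in ITT, scored 0 | 0.436 | 0.426 | 0.401 |
| Replaced and not scored | 0.450 | 0.450 | 0.450 |

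Scoring 0 instead of observing them lowers the arm mean by 0.48w = 0.013, 0.024, 0.048 weeks. If they would have done like the average active participant, the loss is 1.64w = 0.046, 0.082, 0.164 weeks.

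**The case against.** The best case against has four parts.

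- **Stopping is generally not withdrawal.** A reader might infer that any device stop ends participation. The documents do not support that. Study design and Randomization and blinding let participants stop when they choose, and Participant selection criteria treats ending stimulation and dropping out as separate events. Only the under-1-hour rule is automatic. Reasons 1, 3 and 5 are discretionary; reason 3 has a clinical trigger, and reason 5 may largely describe people who never reach the COWS threshold. Since stopping is allowed, reason 1 should seldom apply after the first hour. All of this stands and limits the scope.
- **The plan already covers the gap.** Populations for analysis keeps everyone randomized, and missing weeks count as non-abstinent. A reader might also infer that replacement removes the original participant; the text does not say so, and the projected 125 leaves room for additions. This holds only if the 1-hour entry condition is ignored, and the plan does not say which statement governs.
- **Imputation may often be right.** Withdrawn participants receive usual care, possibly MOUD, which this endpoint counts as non-abstinence. This is fair, and it is one reason the expected effect is small.
- **Early stopping may be rare.** It may be, since 5% is an upper bound. That bears on size, not on the contradiction.

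It is also tempting to say that the rule favours one arm. Only the active arm receives current, so stopping could differ by arm, but the documents give no data by arm.

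**Conclusion.** The concern holds in a limited form. For participants who stop before 1 hour, the plan both withdraws them and gives contradictory instructions on whether they are in ITT. For those past 1 hour, it allows investigator withdrawal from the whole study on grounds that bear mainly or partly on the intervention. Either route loses an outcome that could be observed, and the first may also lose the participant from the comparison.

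The size is probably small. If ITT is kept as everyone randomized, following people instead of scoring zero matters by about 0.01 to 0.05 weeks in the affected arm, provided they do like sham. One-arm withdrawal at up to 10% would move an effect size of 0.45 to between 0.401 and 0.471, in a direction that cannot be known in advance. These figures rest on the pilot SDs, on the raw SD standing in for the adjusted one, and on an assumed 10% ceiling.

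The change is worth making because it settles the analysis population and safety follow-up at little cost, not because a large bias has been shown.

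**What to change.** **(a) Analysis set.** Delete the 1-hour entry condition under Missing data, so that ITT means everyone randomized, as under Populations for analysis. State that replacements are additions and remove no one. Keep the 1-hour condition for the per-protocol set only.

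**(b) Follow-up.** In Study design and Participant withdrawal, state that a stop before 1 hour, and reasons 1, 3 and 5 when they arise after randomization, end device use only. Weekly TLFB, oral fluid tests and adverse-event collection continue to outpatient week 12 unless consent is withdrawn or reason 2 applies. Decisions on device use stay with the investigator, and dis-enrolment before randomization is unaffected.

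**Cost.** This is wording in three places, plus 12 weekly calls and kits per retained participant. At 5% of 125 that is 6.25, or about 6 people, and 6.25 × 12 = 75 calls; anyone retained under reasons 1, 3 and 5 adds 12 each. There is also slight dilution from participants with little or no exposure: 0.450 falls to 0.442, 0.435 or 0.420 at 2.8%, 5% or 10% if active-arm stoppers do like sham. The per-protocol set still shows the comparison among those exposed.
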